6.3.1.2 Elevations in serum creatinine

Serum creatinine must be monitored during the study as stated in visit schedule, refer to [Table 7-1](#).

For pediatric patients the following dose adjustment guidance applies:

- At single increase in serum creatinine (SCr) $>\text{ULN}$ and increased by $\geq 33\%$ from baseline, maintain DFX dose level and repeat the assessment at next visit as clinically indicated.
- If serum creatinine (SCr) $>\text{ULN}$ and increased by $\geq 33\%$ from baseline on 2 consecutive visits, deferasirox dose reduction by 7 mg/kg/day for the FCT is required.
- If after dose reduction, resolution of serum creatinine occurs ($<33\%$) and within normal limits, dose can be re-escalated to 100% of the last dose.

If increase in serum creatinine recurs again within 2 months according to guidelines above, therapy needs to be reduced to 50% of the last dose.

After 2 months, if the serum creatinine increase does not recur, study medication may be re-escalated to 100% of the last dose depending on the clinical judgement of the investigator.

If after an initial dose reduction, a progressive increase in serum creatinine beyond the ULN is observed, or SCr increase recurs, repeat at adequate dose, a treatment interruption is recommended.

After a treatment interruption, if serum creatinine falls below the age-appropriate ULN on two consecutive visits, it is recommended to resume therapy at 50% of the last dose, and after 1 month, if the serum creatinine increase does not recur, study medication can be returned to

100% of the last dose (including body weight adjustment if required) depending on the clinical judgement of the investigator.

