6.3.1.3 Changes in creatinine clearance

Pediatric patient who met the eligibility criteria and who experience a renal function decrease $<\text{LLN}$ ($\text{CrCl} < 90 \text{ ml/min}$) at 2 consecutive visits and the decrease cannot be attributed to other causes, DFX must be dose reduced by 7 mg/kg/day.

If after dose reduction the renal function increases $>\text{LLN}$ ($\text{CrCl} > 90 \text{ ml/min}$), dose may be re-escalated to the last daily dose prior dose reduction depending on the clinical judgement of the investigator.

If after dose reduction the renal function remains $<\text{LLN}$ ($\text{CrCl} < 90 \text{ ml/min}$), treatment must be interrupted. Treatment may be reinitiated depending on the clinical judgement of the investigator.

If creatinine clearance falls below 60ml/min study treatment must be discontinued.

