6.3.1.12 Gastrointestinal disturbances

Some basic recommendations, based on practical experience, can be made to guide investigators in managing subjects who experience diarrhea.

At the first sign of diarrhea, consider anti-diarrhea medication such as loperamide.

Remind the subject to discontinue any laxative preparations or stool softeners.

Eat small, frequent meals. Determine if the subject is lactose intolerant. Note that deferasirox FCT does not contain lactose. Remind the subject to drink an adequate amount of clear liquid per day.

Patients with GI symptoms (including abdominal pain, nausea, vomiting, and diarrhea) and/or patients who are unable to tolerate once a day study drug dosing, the following treatment management steps are recommended in the order specified below:

- Change the timing of study drug administration from morning to evening, and in addition, try using an anti-diarrheal agent for 2 days in case of diarrhea
- If symptoms still continue, try administering the daily dose as a split dose twice daily.

[figure not shown]
Once symptoms resolve, twice daily dosing should be switched back to once daily.

Do not split dose if only prescribing one tablet per day.

- Should the GI issues persist, study drug may be discontinued if the investigator believes it is in the best interest of the patient.

Table 6-4 Criteria for dose reduction / interruption and re-initiation of deferasirox treatment for adverse drug reactions

Recommended dose modifications for deferasirox	
Body weight	
Increase/decrease of weight by >10% compared to baseline weight or body weight at last dose adjustment due to change in patient's body weight	
Dose of study medication needs to be adapted using Deferasirox FCT Weight Dose Table
 
Dose adjustment needed for Weight changes >10% compared to baseline weight or if there is a change in patient's body weight since last dose adjustment.
 
Smaller variations in body weight (<10%) during study, do not require dose adjustments. In this case, baseline body weight can be used to calculate correct dose.

Investigations (Renal)	
Serum creatinine and/or creatinine clearance	
Single increase in serum creatinine $\geq 33\%$	Maintain dose level and repeat the assessment at next visit as clinically indicated

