Single serum creatinine increase $\geq 33\%$ above baseline value and $> \text{ULN}$	
Deferasirox dose reduction by 7 mg/kg/day for the FCT is necessary.
 
If after dose reduction, resolution of serum creatinine occurs (<33%) and within normal limits, dose can be re-escalated to 100% of the last dose.
 
If increase in serum creatinine recurs again within 2 months according to guidelines above, therapy needs to be reduced to 50% of the last dose
 
After 2 months, if the serum creatinine increase does not recur, study medication may be re-escalated to 100% of the last dose depending on the clinical judgement of the investigator.
 
If after an initial dose reduction, a progressive increase in serum creatinine beyond the ULN is observed, or SCr increases re-occur repeatedly at adequate dose, a treatment interruption is recommended.
 
After a treatment interruption, if serum creatinine falls below the age-appropriate ULN on two consecutive visits, it is recommended to resume therapy at 50% of the last dose, and after 1 month, if the serum creatinine increase does not recur, study medication can be returned to 100% of the last dose (including body weight adjustment if required) depending on the clinical judgement of the investigator.

Patients who met the eligibility criteria and who experience a renal function decrease $< \text{LLN}$ ($\text{CrCl} < 90 \text{ml/min}$) at 2 consecutive visits	
If decrease cannot be attributed to other causes, DFX must be dose reduced by 7mg/kg/day.
 
If after dose reduction the renal function increases $>$

Recommended dose modifications for deferasirox

LLN (CrCl >90ml/min), dose may be re-escalated to the last daily dose prior dose reduction depending on the clinical judgement of the investigator.
If after dose reduction the renal function remains <LLN (CrCl <90ml/min), treatment must be interrupted.
Treatment may be reinitiated depending on the clinical judgement of the investigator.
If creatinine clearance falls below 60ml/min study treatment must be discontinued.

Investigations (Hepatic)**Isolated direct (conjugated) Bilirubin elevation**

> ULN – 1.5 x ULN

Maintain dose level

> 1.5 - 3.0 x ULN

Omit dose with weekly monitoring of LFTs, or more frequently if clinically indicated, until resolved to \leq 1.5 x ULN.

If resolved in \leq 14 days, then maintain dose level

If resolved in > 14 days, then dose reduction of 3.5 or 7 mg/kg/day for deferasirox FCT.

> 3.0 - 10.0 x ULN

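### For one raised creatinine value, Section 6.3.1.2 keeps the dose and Table 6-4 cuts it by 7 mg/kg/day; the protocol does not say which governs

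*Protocol*

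**What the plan says.** The trigger in question is one serum creatinine value that is both at least 33% above baseline and above the ULN.

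- **Protocol Section 6.3.1.2.** After a single such value: "maintain DFX dose level and repeat the assessment at next visit as clinically indicated". A reduction follows only when both conditions hold "from baseline on 2 consecutive visits, deferasirox dose reduction by 7 mg/kg/day for the FCT is required".
- **Protocol Table 6-4, first creatinine row.** For a single rise of at least 33%, with no ULN condition: "Maintain dose level and repeat the assessment at next visit as clinically indicated".
- **Protocol Table 6-4, second creatinine row.** The label begins "Single serum creatinine increase" and adds both conditions, at least 33% above baseline and above the ULN. The action is "Deferasirox dose reduction by 7 mg/kg/day for the FCT is necessary". The table has no creatinine row for two consecutive visits.

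Two sentences link text and table. Section 6.3.1 says the modifications are summarized in Table 6-4 and forbids departures from mandatory ones. Section 6.1.4 says most modifications are covered in Section 6.3, with further detail in the table. The Protocol summary (study design) says dose adjustments follow the EU label, which neither document reproduces.

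**The concern.** Two parts of the current protocol give opposite instructions for the same laboratory result. One site can keep the dose until the next test while another cuts it the same day, and each can point to the protocol. Creatinine is measured weekly in the first month and about every four weeks afterwards (Section 7.2.2.5.2), so the two instructions can stay apart for up to four weeks unless the investigator uses an unscheduled check (Section 7.1.9).

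Several reported results depend on which instruction is followed:

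- the count of patients with dose reductions (SAP 2.6.4);
- the table of AEs requiring dose adjustment or interruption (SAP 2.11.1);
- whether the value is an AE at all. Under Protocol 8.1.2.1 a laboratory abnormality that requires a change in study treatment is an AE. If the dose is kept, the value is an AE only when it is clinically significant, symptomatic or treated.

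AE frequency is a secondary endpoint in a study commissioned to characterize safety in this age group.

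**Working it through.** **Step 1: is the conflict real?** The two places side by side:

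| Finding | Section 6.3.1.2 | Table 6-4 |
|---|---|---|
| One value, at least 33% up, not above ULN | no rule | keep dose, repeat |
| One value, at least 33% up and above ULN | keep dose, repeat | reduce by 7 mg/kg/day |
| Same on 2 consecutive visits | reduce by 7 mg/kg/day | no row |

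For the middle row the change is 0 mg/kg/day in the text and -7 mg/kg/day in the table. Both are current text, not part of the amendment summary. In the extracted table each of these row labels sits beside its action, so broken extraction does not explain the difference.

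**Step 2: does anything settle which rule is meant?**

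- For the text: the parallel creatinine clearance rule waits for two visits in both places. Section 6.3.1.3 acts on a value below 90 mL/min "at 2 consecutive visits and the decrease cannot be attributed to other causes, DFX must be dose reduced by 7 mg/kg/day". The matching Table 6-4 row also requires 2 consecutive visits, and then: "If decrease cannot be attributed to other causes, DFX must be dose reduced by 7mg/kg/day".
- For the table: its two creatinine rows form a coherent two-tier scheme, in which a 33% rise alone means watch and a 33% rise above the ULN means reduce.
- Linking sentences: a summary (Section 6.3.1) would yield to the text, but a source of further detail (Section 6.1.4) would not. They pull in opposite directions.

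The question stays open.

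**Step 3: how large is the cut for one child?** Doses are rounded to whole tablets (Section 6.1.1), and SAP 2.6.1 computes actual dose as milligrams divided by weight, so the nominal halving from 14 to 7 mg/kg/day is not what every child would experience. Using Table 6-1, cut = (dose at 14 - dose at 7) / dose at 14:

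| Weight (kg) | At 14 mg/kg/day | At 7 mg/kg/day | Cut |
|---|---|---|---|
| 10-16 | 180 mg | 90 mg | 90/180 = 50% |
| 17-19 | 270 mg | 90 mg | 180/270 = 67% |
| 20-22 | 270 mg | 180 mg | 90/270 = 33% |
| 23-28 | 360 mg | 180 mg | 180/360 = 50% |

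Patients on prior deferasirox may enter needing only 7 mg/kg/day (inclusion criterion 4). For them 7 - 7 = 0, so the whole dose is removed. From 10.5 mg/kg/day the cut leaves 3.5 mg/kg/day, for which Table 6-1 has no tablet below 19 kg.

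**Step 4: how many children?** The documents do not give the frequency of single exceedances. The nearest figure is 3.1% in the five-year observational pediatric study (Section 1.2.1.2), but it counts rises above 33% and above the ULN on at least two consecutive occasions, so it does not measure the single-value trigger.

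**The case against.** The strongest reply is that little hangs on this. Creatinine is checked often, unscheduled tests are allowed, and the creatinine clearance rules, including the stop below 60 mL/min, agree in text and table. All of that stands and limits the safety consequence. It does not tell a site what to do with the value in hand.

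Four stronger readings are tempting, and the documents do not carry them.

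- **The table row is simply a slip.** The clearance rule points that way, but the two-tier reading of the table is equally coherent. The SAP notable criterion for creatinine (two consecutive measurements, Table 2-1) does not help. It is a reporting threshold, and for creatinine clearance it already departs from the dosing rule: the SAP wants two values below 60 mL/min, while the protocol stops treatment once clearance falls below 60, with no repeat required.
- **A fixed loss of dose intensity.** If the repeat is normal 28 days later and the full dose then resumes, a nominal 14 mg/kg/day patient loses 28 x 7 = 196 of 168 x 14 = 2,352 mg/kg, or 8.3%. An 18 kg child actually takes 270/18 = 15 and then 90/18 = 5 mg/kg/day, and loses 28 x 10 = 280 of 168 x 15 = 2,520 mg/kg, or 11.1%. The loss depends on weight, timing, any earlier repeat and whether the dose is restored. At week 24 treatment ends, so no reduction arises.
- **The table's cut is optional because its heading reads** "Recommended dose modifications for deferasirox". The same heading covers rows in which treatment must be discontinued, and Section 6.3.1 allows for both recommended and mandated changes. The row's own wording is the better guide.
- **The primary result is biased.** Section 1.2.1.2 describes GI reactions as dose-dependent, so a reader might infer this. But the primary endpoint's definition and analysis do not refer to the creatinine rule, and nothing in the documents sizes an indirect effect.

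**Conclusion.** The inconsistency is confirmed and should be fixed. For one creatinine value at least 33% above baseline and above the ULN, the protocol requires two incompatible actions and sets no precedence. Which was intended cannot be determined without the EU label or the sponsor.

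For an affected child at 14 mg/kg/day the difference is a 33% to 67% cut against no change, assuming tablets are dispensed as in Table 6-1; at 7 mg/kg/day it is the entire dose. The number of children affected cannot be estimated. Dosing, dose-reduction summaries, AEs requiring dose adjustment and AE classification are exposed. The primary GI endpoint, the SAP notable-value counts and the sample size are not.

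Two lesser mismatches suggest that text and table were not fully reconciled. At first occurrence, UPCR above 1.0 mg/mg interrupts treatment after two consecutive samples in Section 6.3.1.5, while Table 6-4 appears to act on one. That part of the table is badly broken in extraction, and Section 6.3.1.5 itself uses one sample for recurrence, so little weight should rest on it. For serum ferritin below 500 ng/mL, interruption is recommended in Section 6.3.1.4 and required in Table 6-4.

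**What to change.** The sponsor should confirm the intended rule against the EU label and make both places identical.

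- **If the two-visit rule is intended:** change the Table 6-4 reduction row to a rise of at least 33% above baseline and above the ULN on 2 consecutive visits, and apply the keep-and-repeat row to a single such value.
- **If the stricter single-value rule is intended:** amend Section 6.3.1.2 to match the table.
- **In either case:** state what to do when a 7 mg/kg/day cut leaves no dispensable dose, for example at 7 mg/kg/day, or at 10.5 mg/kg/day below 19 kg. Section 6.1 offers only a written request to the sponsor for low-weight, low-dose patients.
- **In the same amendment:** align the UPCR above 1.0 trigger, separating first occurrence from recurrence, and use one action word for serum ferritin below 500 ng/mL.

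The cost is a wording amendment, which needs ethics committee approval under Section 12.1, and notice to sites; seven patients were already enrolled at Amendment 1. Visits, data collection, SAP endpoints and sample size do not change.

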6.3.1.3 Changes in creatinine clearance

Pediatric patient who met the eligibility criteria and who experience a renal function decrease $<\text{LLN}$ ($\text{CrCl} < 90 \text{ ml/min}$) at 2 consecutive visits and the decrease cannot be attributed to other causes, DFX must be dose reduced by 7 mg/kg/day.

If after dose reduction the renal function increases $>\text{LLN}$ ($\text{CrCl} > 90 \text{ ml/min}$), dose may be re-escalated to the last daily dose prior dose reduction depending on the clinical judgement of the investigator.

If after dose reduction the renal function remains $<\text{LLN}$ ($\text{CrCl} < 90 \text{ ml/min}$), treatment must be interrupted. Treatment may be reinitiated depending on the clinical judgement of the investigator.

If creatinine clearance falls below 60ml/min study treatment must be discontinued.

6.3.1.4 Changes in serum ferritin

Serum ferritin must be monitored as stated in visit evaluation schedule, see [Table 7-1](#).

For iron chelation naïve subjects study entry dose adjustments are allowed after 4 weeks on study based on serum ferritin and investigator's judgement. For iron-chelation pre-treated

subjects, the dose of deferasirox should be adjusted if necessary every 3 months based on the trends in serum ferritin and investigator's judgement.

Dose adjustments should be made in steps of 3.5 or 7 mg/kg/day and are to be tailored to the individual patient's response and therapy goals (maintenance or reduction of iron burden). In patients not adequately controlled with deferasirox, doses of up to 28 mg/kg/day may be considered. Deferasirox dose above 28 mg/kg/day is not allowed.

In patients whose SF level has reached the target (usually between 500 and 1000 ng/mL), dose reductions in steps of 3.5 or 7 mg/kg/day are recommended to maintain SF levels within the target range. If SF falls below 500 ng/mL, an interruption of study treatment is recommended until SF rises above 500 ng/mL.

6.3.1.5 Changes in urine protein/creatinine ratio

Proteinuria must be monitored as stated in visit evaluation schedule see [Table 7-1](#).

For patients who develop proteinuria or a worsening of pre-existing proteinuria (assessed by a dipstick) at any visit, microscopic urine assessment should be performed.

In case of a single increase of the UPCR by quantitative urinalysis measurement, the assessment should be repeated at the next visit. Deferasirox dose reduction by 50% is recommended if the UPCR increases to >0.5 (mg/mg) in two consecutive non first void urine samples (a minimum of 48 hours apart), if all other causes of proteinuria have been excluded.

Deferasirox must be temporarily interrupted if the UPCR ratio increases to >1.0 (mg/mg) in two consecutive non first void urine samples (a minimum of 48 hours apart).

After resolution (<0.5 mg/mg), dose can be resumed again at 100%.

If increase in UPCR >0.5 mg/mg recurs again within 2 months, study drug needs to be reduced to 50% of the last dose. After 2 months, if increase in UPCR does not recur, study medication can be returned to 100% of the last dose.

If increase recurs in UPCR (> 1.0 (mg/mg) recurs in one single non-first void urine samples: Interrupt study treatment.

After resolution (≤ 0.5 mg/mg), dose can be resumed again at 50% of the last dose after 1 month, if increase in UPCR does not recur for another month, study medication can be returned to 100% of the last dose.

Should proteinuria persist, study treatment may be discontinued if the investigator believes it is in the best interest of the patient. Novartis may be contacted by the investigator to discuss dosing options if the investigator so desires.

Dose adjustment will be based on laboratory results.

6.3.1.6 Skin disorders

6.3.1.6.1 Stevens - Johnson syndrome and other severe skin reactions

Severe skin reactions, including Stevens-Johnson syndrome have been reported during deferasirox therapy. If Stevens-Johnson syndrome is suspected, study treatment must be

immediately discontinued and not reintroduced. The risk of other severe skin reactions (toxic epidermal necrolysis [TEN], drug-reaction with eosinophilia and systemic symptoms [DRESS]) cannot be excluded. If Stevens Johnson syndrome or any other severe skin reaction is suspected, deferasirox must be discontinued immediately and not reintroduced. Further management is at the discretion of the investigator.

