6.3.1.6.2 Skin Rash (other than e.g. SJS, TEN, DRESS)

For skin rash of mild/moderate severity (defined as those causing minimal symptoms which require no or minimal supportive treatment), deferasirox drug should be continued without dose adjustment. The skin rash may resolve spontaneously without further intervention.

If the rash persists for >1 week or becomes more severe, treatment with deferasirox will be interrupted. After the rash resolves, resume deferasirox at 50% of the subject's last dose, If the rash does not recur, increase dose back to 100% of the subject's dose after 2 weeks.

For a severe rash (distressing symptoms requiring discontinuation and/or systemic steroids), discontinue treatment until resolution of rash. Once the rash has resolved, resume at 50% of subject's dose. If necessary, a brief course of oral steroids may be given concurrently with resumption of deferasirox. If the rash does not recur, increase by steps of 3.5 mg/kg day deferasirox FCT every 2 weeks until the subject's last dose is achieved.

Rare cases of erythema multiforme (EM) have been reported during deferasirox treatment. Cases if suspected EM must be reported and DFX dose adjusted in accordance with the above recommendations for severe rash.

If rash recurs, study drug may be discontinued if the investigator believes that is in the best interest of the patient.

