Severe skin reactions, including Stevens-Johnson syndrome (SJS), Toxic epidermal necrolysis (TEN), DRESS	Must be reported if occurs during Exjade therapy. If SJS ,TEN, DRESS is suspected, study treatment must be immediately discontinued and not be reintroduced
Skin Rash (other than SJS, TEN, DRESS)	
For skin rash of mild/moderate severity (defined as those causing minimal symptoms which require no or minimal supportive treatment)	Study drug should be continued without dose adjustment. The skin rash may resolve spontaneously without further intervention. If the rash persists for >1 week or becomes more severe, treatment with study drug will be interrupted. After the rash resolves, resume study drug at 50% of patient's last dose. If the rash does not recur, increase dose back to 100% of patients dose after 2 weeks. Discontinue treatment until resolution of rash. Once the rash has resolved, resume at 50% of patient's dose. If necessary, a brief course of oral steroids may be given concurrently with resumption of study drug. If the rash does not recur, increase by steps of 3.5 mg/kg/day for deferasirox FCT every 2 weeks until patient's last dose is achieved. If the rash recurs, study treatment may be discontinued if the investigator believes that it is in the best interest
Severe rash (distressing symptoms requiring discontinuation and/or systemic steroids)	

Recommended dose modifications for deferasirox

of the patient.

Novartis may be contacted by the investigator to discuss dosing options if the investigator so desires

Dose modification criteria for auditory and ocular disturbances

Auditory (decreased hearing) and ocular (lens opacities) disturbances have been reported with deferasirox treatment.

Auditory and ophthalmic testing is required before the start of deferasirox treatment.

If disturbances are noted dose reduction or interruption may be considered and a repeated testing performed as per investigator's judgment.

Dose modification criteria for hypersensitivity reactions

Cases of serious hypersensitivity reactions (such as anaphylaxis and angioedema) have been reported in patients receiving deferasirox, with the onset of the reaction occurring in the majority of cases within the first month of treatment.

If reactions are severe, deferasirox should be discontinued and appropriate medical intervention instituted.

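### A severe rash or suspected erythema multiforme can meet both a never-restart and a restart rule, and a rash that worsens to severe fits two re-escalation schedules

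*Protocol*

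**What the plan says.** The protocol governs skin events in several places.

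- **Section 6.3.1.6.1** names two reactions besides SJS: "The risk of other severe skin reactions (toxic epidermal necrolysis [TEN], drug-reaction with eosinophilia and systemic symptoms [DRESS]) cannot be excluded". It then gives the rule: "If Stevens Johnson syndrome or any other severe skin reaction is suspected, deferasirox must be discontinued immediately and not reintroduced".
- **Section 6.3.1.6.2** is headed "Skin Rash (other than e.g. SJS, TEN, DRESS") and has two paths. On the first, a mild or moderate rash is treated through without a dose change, but "If the rash persists for >1 week or becomes more severe, treatment with deferasirox will be interrupted". Dosing then resumes at half the last dose and returns to the full dose after 2 weeks if the rash stays away. The second path reads: "For a severe rash (distressing symptoms requiring discontinuation and/or systemic steroids), discontinue treatment until resolution of rash". It too resumes at half dose, then climbs by 3.5 mg/kg/day every 2 weeks to the last dose.
- **Section 6.3.1.6.2 on EM**: "Cases if suspected EM must be reported and DFX dose adjusted in accordance with the above recommendations for severe rash".
- **Table 6-4, severe skin reactions**: the row label is open-ended, since it speaks of severe reactions as including the three named ones. The action cell names only SJS, TEN and DRESS: if one of these "is suspected, study treatment must be immediately discontinued and not be reintroduced".
- **Table 6-4, skin rash**: the rows repeat both rash paths. Their label excludes SJS, TEN and DRESS without the qualifier e.g. The table as provided has no EM entry.
- **Section 6.3.1** makes permanent discontinuation mandatory for events marked that way in Table 6-4 or listed in section 7.1.5. Section 7.1.5 gives general reasons for stopping and names no skin reaction.

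**The concern.** The no-restart rule in section 6.3.1.6.1 is open at its edge, and so is the exclusion in the heading of section 6.3.1.6.2. Neither section says whether a rash bad enough to need systemic steroids, or a suspected EM, counts as a severe skin reaction. A site that reads section 6.3.1.6.1 literally stops for good. A site that turns to section 6.3.1.6.2 or Table 6-4 restarts a severe rash at half dose.

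What is at stake is re-exposure of a child aged 2 to under 6 in a study whose main purpose is safety. The reported results would also shift. Under one reading the event is a permanent discontinuation. Under the other it is an interruption with dose change. SAP section 2.11.1 tabulates these separately, and exposure after the event differs too.

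A second, smaller gap concerns a rash that starts mild or moderate and worsens until it meets the severe description. Section 6.3.1.6.2 then offers two ways back to full dose and does not say which one governs.

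**Working it through.** The documents state no figure to reproduce. The check compares the rules event by event, then works out how far apart the two re-escalation schedules lie.

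**Step 1. Restart rules side by side**

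| Suspected event | 6.3.1.6.1 | 6.3.1.6.2 | Table 6-4 |
|---|---|---|---|
| SJS, TEN, DRESS | no restart | excluded by heading | no restart |
| Severe rash, none of these three | no restart if it counts as a severe skin reaction (undefined) | restart at 50% | restart at 50% |
| EM | no restart if it counts as a severe skin reaction (undefined) | restart at 50%, as severe rash | no entry as provided |

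The first row agrees throughout. In the second and third rows the answer turns on a definition that the protocol does not give. Text and table also differ in scope: section 6.3.1.6.1 reaches beyond the three names, and the action cell of Table 6-4 does not.

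**Step 2. Which schedule applies to a worsening rash**

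Worsening from mild to moderate stays on the first path. A rash that is severe from the outset, or a suspected EM, is on the second path only. A rash that begins mild or moderate and worsens to severe meets the entry condition of both.

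**Step 3. Time from restart to full dose**

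Inputs: restart at 50% on both paths; full dose after 2 weeks on the first; steps of 3.5 mg/kg/day every 2 weeks on the second (section 6.3.1.6.2); maximum dose 28 mg/kg/day (section 6.3.1.4).

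Assumptions, not in the documents: the first step comes 2 weeks after restart, the last step is cut to the last dose, and rounding to tablet strengths is ignored.

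For last dose D, the second path takes 2 × ⌈(D − D/2) / 3.5⌉ weeks.

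| D (mg/kg/day) | D/2 | (D/2)/3.5 | Steps | First path (weeks) | Second path (weeks) |
|---|---|---|---|---|---|
| 7 | 3.5 | 1 | 1 | 2 | 2 |
| 10.5 | 5.25 | 1.5 | 2 | 2 | 4 |
| 14 | 7 | 2 | 2 | 2 | 4 |
| 17.5 | 8.75 | 2.5 | 3 | 2 | 6 |
| 21 | 10.5 | 3 | 3 | 2 | 6 |
| 24.5 | 12.25 | 3.5 | 4 | 2 | 8 |
| 28 | 14 | 4 | 4 | 2 | 8 |

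The paths coincide at 7 mg/kg/day and differ from 10.5 mg/kg/day upward. At the targeted starting dose of 14 mg/kg/day (Table 6-3) the difference is 2 weeks. At the maximum dose it is 6 weeks, and the longer path takes 8 of the 24 treatment weeks.

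**The case against.** The best defence is that the two sections are meant for different conditions. TEN and DRESS stand in brackets in section 6.3.1.6.1, and the wider phrase in the next sentence can be read back to them. The heading of section 6.3.1.6.2 sets the same reactions aside, and both skin entries in Table 6-4 use the same three names. Section 6.3.1 points to Table 6-4 for mandatory permanent discontinuation, so the table could be taken to fix the boundary. EM is expressly assigned to the severe-rash path. Different speeds for different severities are a normal design.

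Much of this stands. It shows the probable intent, and it removes any conflict for SJS, TEN and DRESS. It does not close the gap. Section 6.3.1.6.1 carries its own mandatory wording and reaches past the three names, the heading's exclusion is only by example, and the table's row label is open as well. A site cannot tell from the page that a severe rash lies outside the no-restart rule. The assignment of EM is explicit in one subsection but missing from the table as provided.

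A reader might go further and infer that severe rash and EM themselves have two competing speeds. They do not: each has the 3.5 mg/kg/day schedule only. A reader might also hold the severe-rash instruction to the glossary, which treats discontinuation of study treatment as permanent. The instruction is "discontinue treatment until resolution of rash. Once the rash has resolved, resume at 50% of subject's dose", which cannot be taken as permanent.

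**Conclusion.** The point holds as a conflict of scope between two re-exposure rules, with a narrower overlap in re-escalation. Read literally, a severe rash or suspected EM can meet both a no-restart and a restart rule, and text and table draw the no-restart line in different places. A rash that worsens to severe has two schedules. On the assumptions stated, these differ by 0 weeks at 7 mg/kg/day, 2 at 14, 4 at 21 and 6 at 28.

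The number of children affected cannot be computed. A reader might apply the 5.0% rate of suspected drug-related rash in section 1.2.1.2 to the 40 planned patients. That rate covers all severities and comes from a 5-year observational study of the dispersible tablet with mean exposure of 44.1 months (section 1.2), so it does not carry over to severe rash in 24 weeks of crushed film-coated tablets. Few events are expected: the enrolment target is small and section 6.3.1.6.2 describes EM as rare. The primary endpoint (SAP section 2.8.1) rests on gastrointestinal terms and is not defined by any skin rule.

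The weight therefore lies in the consequence for a single child rather than in frequency. That is enough to call for correction, because sites following different parts of the same protocol could act in opposite ways on re-exposure.

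**What to change.** Reconcile sections 6.3.1.6.1 and 6.3.1.6.2 with the skin entries of Table 6-4:

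1. Define *severe skin reaction* and *severe rash* so that no event falls under both, and use the same list in text and table.
2. Confirm which group suspected EM belongs to, make section 6.3.1.6.1 consistent with that, and add EM to Table 6-4.
3. State which re-escalation schedule governs a mild or moderate rash that worsens until it meets the severe description.

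The clinical team decides which rule stands in each case; this review takes no position on it. The cost is wording in two subsections and the matching table rows, through an amendment and a notice to sites. No new procedure, visit or data item is needed.
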